4.2.3 Visit Windows

Visit windows will not be employed in the analysis, i.e., data will not be excluded from the analysis based on whether the data fell outside of visit windows.

4.2.4 Multiplicity

There will be no multiplicity adjustments in this Phase 2a pilot study.

4.2.5 Baseline Definition

Baseline will be determined separately for each efficacy endpoint and safety parameter. That is, a missing baseline for one endpoint/parameter does not mean that the baseline will be missing for the other endpoints/parameters. For endpoints with discrete visits, baseline will use the last observation prior to dosing.

The baseline for each of the analysis periods is specified below:

Period 1 Baseline = Screening/Day 1 (based on assessment)

Period 2 Baseline = Day 15

Period 3 Baseline = Day 42

Period 4 Baseline = Day 56

where Days 15, 42, and 56 refer to the baseline of the respective period and not the actual study day for any one patient.

Change from baseline is defined as:

Period 1 (Day 15 value – Day 1 value)

Period 2 (Day 42 value – Day 15 value)

Period 3 (Day 56 value – Day 42 value)

Period 4 (Day 70 value - Day 56 value)

For patients with either a continuous active or a continuous placebo dosing over time, information may be summarized using the following intervals:

Period 2/3: Day 15 through Day 56

Continuous low dose: Day 15 through Day 56

Continuous high dose: Day 15 through Day 70

Continuous placebo: Day 1 through Day 56

4.3 Statistical Hypothesis

For the co-primary efficacy endpoint, the null hypothesis is that the mean percent change from baseline (Period 2) in Weight (kg) for patients taking RM-493 is the same as for those taking placebo. That is,

$$H_{p0}: \mu_{pA} = \mu_{pP}$$

$$H_{p1}: \mu_{pA} \neq \mu_{pP}$$

where μ_{pA} and μ_{pP} is the mean percent change in weight (kg) at Day 42 (Week 6), for patients on active treatment (RM-493 0.5 mg and placebo 50 uL) and (RM-493 1.5 mg and placebo150 uL), respectively.

Likewise, for the co-primary efficacy endpoint for the PWS, the null hypothesis is that the mean percent change from baseline (Period 2) in the Overall Score for the Dykens PWS assessment for patients taking RM-493 is the same as for those taking placebo. That is,

$$H_{s0}: \mu_{sA} = \mu_{sP}$$

$$H_{s1}: \mu_{sA} \neq \mu_{sP}$$

where μ_{sA} and μ_{sP} is the mean percent change in the PWS Overall score at Day 42 (Week 6), for patients on active treatment (RM-493 0.5 mg and placebo 50 uL) and (RM-493 1.5 mg and placebo150 uL), respectively.

4.4 Study Patients

Screen Failure: A patient screened for participation in the RM-493-010 study who does not meet all of the inclusion and/or who meets any of the exclusion criteria for enrolment will be deemed a screen failure and will not be randomized.

Patients may also be considered screen failures during the 14-day, single-blind, placebo run-in phase. After an initial screening and confirmation of eligibility, volunteers will enter a two-week single blind placebo run-in period (period 1). Those who are compliant in study drug administration and have demonstrated willingness to complete study procedures (weighing, questionnaire and diary completion), will be randomized to receive subcutaneous doses of RM-493 or placebo for 4 weeks of double-blind treatment (primary efficacy timepoint) (period 2).

4.4.1 Disposition of Patients

Summary data will be presented by dose group and overall, based on the number of patients enrolled as well as defined by the analysis populations. Patient disposition will be tabulated and include the number screened and the number who participated in the placebo run-in period. Screen failure data during the placebo run-in period as well as screen failures prior to the placebo run-in period will also be summarized. The number of patients in the ITT Set, Safety Set, the Full Analysis Set, and the Per Protocol Set, and the number who withdrew prior to completing the study along with their primary reason for withdrawal, and the Period

in which they discontinued, will be presented. A breakdown of patients by site and treatment group, within the Safety Set will be provided.

A by-patient listing including the details of the study disposition will be provided for all patients (including screen failures that are prior to or during the single blind run-in period).

4.4.2 Summary of Populations and Protocol Deviations

A summary of the populations and associated defining criteria will be presented in a tabular format for selected populations (ITT, SAF, FAS, PP).

For the ITT population, the number of patients with a protocol violation (determined through joint clinical / statistical review prior to data base lock), as well as a summary of protocol deviation categories will be presented. Protocol deviation categories will be summarized by category and center.

The list of important protocol deviations related to study inclusion/exclusion criteria, patient management/assessment, or conduct of the study will be finalized by the Sponsor and documented prior to database lock or any unblinding of data. Specific criteria will be reviewed prior to database lock, and will include such criteria as contraindicated concomitant medications or incorrect dose group and other items as deemed appropriate by the Sponsor.

All important protocol deviations will be summarized and presented in a by-patient data listing.

4.4.3 Demographic and Disease Characteristics

Demographic data will include patient age, gender, race, and ethnicity. Baseline characteristics include weight, height, BMI, and waist circumference. Demographic and baseline characteristics will be tabulated for all patients in the SAF population by dose group and overall.

A by-patient listing will be presented for all patients in the SAF population.

4.4.4 Study Drug Administration

Study drug exposure will be presented for all patients in the SAF. Injection information will include total study drug exposure, individual administering dose, quantity of dose administered (full or partial), and reason for dose interruption or modification and will be tabulated by period 2 and 3.

Exposure data will be presented in a by-patient data listing for all patients in the SAF population.

4.4.5 Medical History

A by-patient listing of medical history data will be provided in a data listing.

4.4.6 Concomitant Medications

By-patient listings of all concomitant medications will be provided.

4.5 Efficacy Endpoints and Analyses

4.5.1 Primary Efficacy Endpoints

There will be 2 co-primary endpoints analysed.

Percent change from baseline in body weight, and percent change from baseline in the Overall score for the PWS Hyperphagia questionnaire over the 4-week double-blind dosing period (Period 2) will be assessed as co-primary efficacy endpoints.

The **Hyperphagia Questionnaire** is a 10-item instrument designed to measure food-related preoccupations and problems in PWS, as well as the severity of these concerns. Three factors identified from this questionnaire are:

- Hyperphagic Drive (e.g. how persistent in asking for food; how easy to direct away from food; items 1,3,6,9)
- Hyperphagic Behaviors (e.g. how fast or clever in obtaining food; how often steal food; items 2,4,5,8)
- Hyperphagic Severity (time spent talking about food; extent that food interferes with everyday functioning; items 7,10)

Items are rated by care providers on a 5-point scale (1=not a problem to 5=a severe and/or frequent problem). The questionnaire can be found in Appendix 2. Raw scores for each factor will be used in data analyses, and the three domains will be summed for an overall summary index of hyperphagia (maximum overall score of 50). Missing values will not be imputed. If a single item in a factor is missing for a patient, that factor will be missing.

These endpoints will be tabulated by dose group for the FAS and PP populations. There will be no adjustment for multiplicity.

4.5.1.1 Primary Analysis

The primary analysis involves comparison of percent change from baseline during Period 2 between the RM-493 active treatment groups and placebo. A mixed model repeated measures analysis of variance with fixed terms for treatment, time, treatment-by-time interaction and baseline covariate as well as a random effect for subjects will be used to assess the primary efficacy endpoint. An unstructured covariance matrix will be used to model the expected different variances among the treatments. T-tests derived from the model will use Satterthwaite's degrees of freedom estimates.

The assumption of normality will be assessed via the Shapiro-Wilk statistic as a diagnostic of closeness to normality, not as a conditional test associated with efficacy endpoint analyses. Other graphical assessments of residuals from the model fit may be examined. If a substantial departure from normality is observed, a transformation such as log (post/pre) or rank may be used to analyze the data as a sensitivity analysis; however, the analysis on the original scale of observation will be reported.

The comparison of each dose of RM-493 with placebo will be carried out via 1-sided statistical test at alpha=0.05, with no adjustment for multiplicity for comparisons with two dose regimens. Of note, the 0.5 mg dose was included in the study as an anticipated no-effect or minimal effect dose for dose ranging.

Least square (LS) mean changes from baseline for each treatment group, and LS mean difference between each active RM-493 dose group and placebo, and the associated 95% confidence intervals for the difference will be provided, along with the reported p-values (one-sided). In addition change from baseline will be tested using a 2-sided statistical test at alpha=0.05.

Sample SAS code that can be used to implement the MMRM analysis is provided below:

```
proc mixed data=adef method=reml;
  class subjid trtpn visitnum;
  model pcgresn = trtpn visitnum trtpn*visitnum base / solution ddfm=satterthwaite;
  repeated visitnum / type=un subject=subjid;
  lsmeans trtpn*avisitn / cl alpha=0.05;
  lsmeans trtpn*avisitn / diff=control ('1' 'Day x') cl; *[where '1' represents group=placebo];
run;
```

In an effort to examine the robustness of the results obtained from the analysis of the co-primary endpoints, sensitivity analyses will be performed. The sensitive analysis will be undertaken by imputing missing data from subjects who do not adhere to therapy with the mean value from those subjects on the same arm that also did not adhere to therapy, but had the measurement for the primary endpoint.

By-patient data listings will be provided.

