8.5. Statistical Methods

Analyses will be based on observed data only; no data will be imputed.

Continuous efficacy endpoints will be assessed via repeated measures, longitudinal mixed analysis of variance model which will include fixed effects terms for treatment, timepoint, treatment-by-timepoint interaction, and baseline covariate, and random effect for subjects. An unstructured covariance matrix will be used to model the expected different variances among the treatments. T-tests derived from the model will use Satterthwaite's degrees of freedom estimates. The assumption of normality will be assessed via the Shapiro-Wilk statistic as a diagnostic of closeness to normality, not as a conditional test associated with efficacy endpoint analyses. Other graphical assessments of residuals from the model fit may be examined. If a substantial departure from normality is observed, a transformation such as log (post/pre) or rank may be used to analyze the data as a sensitivity analysis; however, the analysis on the original scale of observation will be reported.

The comparison of each dose of RM-493 with placebo will be carried out via 1-sided statistical test at alpha=0.05, with no adjustment for multiplicity for comparisons with two dose regimens. This is justified by the pilot nature of this small study.

AEs will be coded by using the most current version of Medical Dictionary for Regulatory Activities (MedDRA) and summarized by system organ class, preferred term, and treatment group for the number and percent of AEs reported, the number of patients reporting each AE, and the number of patients with any AE.

A by-patient AE data listing including onset and resolution dates, verbatim term, preferred term, treatment, severity, relationship to treatment, action taken, and outcome will be provided.

Safety data including laboratory evaluation and vital signs assessments will be summarized by time of collection and by treatment group. In addition, change from baseline to any post-dose values will be summarized for vital signs and clinical laboratory results. Frequency of patients with abnormal safety laboratory results will be tabulated by treatment.

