4.1 Sample Size Justification

Prior data from the 4 week Phase 1b treatment arms of Study RM493-002 (MAD study) yielded the following summary statistics for mean change from baseline after 4 weeks:

Pooled SD for Placebo:	SD=1.1, N=12
Pooled SD for RM493:	SD=2.3, N=18

Assuming SD=1.1 for placebo and SD=2.3 for RM-493, if the true mean difference in 1-month weight loss between treatments is 2.5 kg in this study (N=12 placebo and N=12 RM493), there would be 94% power to yield a statistically significant (alpha=0.05, 1-sided) difference between treatments (83% power if true difference is 2 kg). The minimum observed difference in mean weight loss after 4 weeks of treatment, between RM493 and placebo that would be statistically significant is 1.3 kg.

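### The dose comparisons are tested one-sided at 5%, but the SAP reports them with 95% intervals, code that prints two-sided p-values and two-sided alternatives, so a significant result can sit beside an interval that includes zero

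*SAP*

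**What the plan says.** Four places in the plan set or imply the sidedness of the primary comparisons.

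- **Decision rule.** Protocol 8.5 states: "The comparison of each dose of RM-493 with placebo will be carried out via 1-sided statistical test at alpha=0.05". SAP 4.5.1.1 repeats the rule.
- **Reported output.** For the LS mean difference of each dose from placebo, SAP 4.5.1.1 says that "the associated 95% confidence intervals for the difference will be provided, along with the reported p-values (one-sided". The text does not call the interval two-sided, but that is the ordinary meaning of a 95% confidence interval.
- **Sample code (SAP 4.5.1.1).** The LS means line is "lsmeans trtpn*avisitn / cl alpha=0.05" and the comparison line is "lsmeans trtpn*avisitn / diff=control ('1' 'Day x') cl". The second has no alpha option, so it gives the software defaults: two-sided p-values and two-sided 95% limits. Both lines name `avisitn`, whereas the CLASS and MODEL statements contain `visitnum`.
- **Hypotheses (SAP 4.3).** The alternatives for percent change in weight and for percent change in hyperphagia score are both written as not equal, that is, two-sided.

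SAP 4.5.1.1 also adds: "In addition change from baseline will be tested using a 2-sided statistical test at alpha=0.05". It does not say whether this is a within-group test of change against zero or a between-group test of the change endpoint.

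SAP 4.1, like Protocol 8.1, bases power on one-sided 5% and gives the smallest observed difference "that would be statistically significant is 1.3 kg".

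**The concern.** A test and the interval shown beside it should lead to the same conclusion. A one-sided 5% test is matched by a two-sided 90% interval, or by a one-sided 95% bound. A two-sided 95% interval is matched by a one-sided 2.5% test. Under the plan as written, every one-sided p between 0.025 and 0.05 produces two outputs that point in different directions, and neither document says how to read such a result.

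The code and SAP 4.3 make this worse. A programmer who follows the code, or a reader who follows SAP 4.3, could defend comparing a two-sided p with 0.05. One who follows the text of 4.5.1.1 would compare a one-sided p with 0.05. SAP section 1 says that the study is meant to give a rationale for a Phase 3 design, so borderline results will be read closely. Settling the sidedness after unblinding would be open to criticism.

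**Working it through.** **Inputs.** SAP 4.1: "Assuming SD=1.1 for placebo and SD=2.3 for RM-493", with 12 patients per arm and true differences of 2.5 and 2.0 kg. Degrees of freedom follow SAP 4.5.1.1: "T-tests derived from the model will use Satterthwaite's degrees of freedom estimates".

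**Step 1: standard error and degrees of freedom.**

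- SE = sqrt(1.1²/12 + 2.3²/12) = sqrt(6.50/12) = 0.736 kg
- df = (1.21/12 + 5.29/12)² / [((1.21/12)² + (5.29/12)²)/11] = 15.8

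**Step 2: reproduce the plan's figures.** The threshold is t × SE, and power comes from the noncentral t.

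| Test | Critical t | Smallest significant difference | Power at 2.5 kg | Power at 2.0 kg |
|---|---|---|---|---|
| One-sided 5% | 1.747 | 1.286 kg | 94.5% | 83.0% |
| Two-sided 5% (one-sided 2.5%) | 2.122 | 1.562 kg | 89.0% | 72.2% |
| Stated in SAP 4.1 | not given | 1.3 kg | 94% | 83% |

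The one-sided row reproduces the plan and the two-sided row does not. Other one-sided variants fit less well: 22 df gives 95.0%, 83.8% and 1.26 kg; the normal approximation gives 96.0%, 85.8% and 1.21 kg.

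**Step 3: the band of disagreement.** The one-sided test is significant from 1.29 kg. The 95% interval excludes zero only from 1.56 kg. The interval half-widths are 1.562 kg (95%) and 1.286 kg (90%).

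| Observed difference | t | One-sided p | Two-sided p | 95% CI | 90% CI |
|---|---|---|---|---|---|
| 1.3 kg | 1.766 | 0.048 | 0.097 | -0.26 to 2.86 | 0.01 to 2.59 |
| 1.5 kg | 2.038 | 0.029 | 0.059 | -0.06 to 3.06 | 0.21 to 2.79 |
| 1.6 kg | 2.174 | 0.023 | 0.045 | 0.04 to 3.16 | 0.31 to 2.89 |

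The SAP's own 1.3 kg threshold lies inside the band. The 90% interval agrees with the one-sided test in every row.

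**Step 4: how often a result falls in the band.** This is the difference between the two powers.

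- True difference 0: 5.0% - 2.5% = 2.5 points
- True difference 1.5 kg: 62.0% - 48.2% = 13.8 points
- True difference 2.0 kg: 83.0% - 72.2% = 10.8 points
- True difference 2.5 kg: 94.5% - 89.0% = about 5.6 points (from unrounded powers)

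**Step 5: reach of the illustration.** The co-primary endpoints are percent changes from a repeated-measures model, not kg changes from a two-sample test. With 2:1:3 allocation of about 20 and then 16 patients, pooled by dose, the expected arms are:

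- placebo: (20 + 16) × 2/6 = 12
- 0.5 mg: 20 × 1/6 = about 3
- 1.5 mg: 20 × 3/6 + 16 × 1/6 = about 13
- 2.5 mg: 16 × 3/6 = 8

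Twelve against twelve therefore resembles only the 1.5 mg comparison. The kg band is an illustration. The disagreement for one-sided p between 0.025 and 0.05 does not depend on the scale or the arm sizes.

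**The case against.** The best defence is that the text of SAP 4.5.1.1 is explicit. It requires one-sided p-values, and the code is offered only as a sample. Halving a two-sided p in the favourable direction gives the one-sided p, so the lower-tail option in the software is one route and not a necessity. The decision rests on the test. Nothing makes the 95% interval a decision rule, and showing it as a measure of precision is a legitimate choice. This is also a pilot without multiplicity adjustment, whose conclusions are to be confirmed in Phase 3.

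Much of this stands. If the text is followed, the nominal 5% one-sided error per comparison holds, and so do the stated power and the 1.3 kg threshold. What remains is that the SAP neither states the conversion nor labels the interval descriptive, and its formal hypotheses in 4.3 contradict the one-sided rule. Pilot status explains the absence of multiplicity adjustment. It does not explain a test and an interval at different levels.

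A reader might also infer that percent change and kg change in the same weights are judged at different error rates, because of the added two-sided test. The documents do not establish this. That sentence follows one about LS mean changes within each group, so it may mean a within-group test. SAP 4.5.2.1 sends kg change to methods similar to those of 4.5.1.1. The sentence is unclear, and that is as far as the point goes.

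**Conclusion.** The inconsistency is real, and it concerns reporting and interpretation. For each dose comparison, a one-sided p between 0.025 and 0.05 would be called significant beside a 95% interval that includes zero. On the planning inputs this covers observed differences of 1.29 to 1.56 kg, with a chance of 13.8, 10.8 and 5.6 points at true differences of 1.5, 2.0 and 2.5 kg. These figures assume SDs of 1.1 and 2.3 kg, 12 per arm, unequal-variance t-tests and a two-sided 95% interval.

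A reader might infer that the study has only 89% and 72% power. The documents do not support that: 94%, 83% and 1.3 kg are correct for the one-sided 5% test on which they are based. The lower figures apply only if the two-sided alternatives in SAP 4.3, or the code's unconverted p-values, were used for the decision.

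The mismatch of `avisitn` and `visitnum` is a separate, smaller slip: the effect requested in LSMEANS is not in the model, so the code would not run as printed.

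**What to change.** Before final unblinding:

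1. In SAP 4.5.1.1, name the two-sided 90% interval (or the one-sided 95% bound) as the interval that matches the test, and label any 95% interval descriptive.
2. State that the two-sided p is converted to one-sided in the direction of benefit, which is a decrease for both co-primary endpoints, or use DIFF=CONTROLL. Use one visit variable throughout the CLASS, MODEL and LSMEANS lines, and set the alpha option to 0.10 where 90% limits are wanted.
3. Rewrite both alternatives in SAP 4.3 as one-sided, to agree with 4.5.1.1.
4. State whether the additional two-sided test of change from baseline is within-group. If it instead means the between-group change endpoint, use the same one-sided 5% rule as for percent change.

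The cost is SAP wording and a few lines of code. No new data are needed, and the sample size and stated power stay as they are. The downside is that a 90% interval is narrower than the customary 95% one and could look like overstated precision, so both should be shown and clearly labelled.

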4.5.2 Secondary Efficacy Endpoints

4.5.2.1 Key secondary efficacy endpoints

Key secondary efficacy endpoints will be analysed for Period 2 for 3 treatment groups (see Table C, Period 2) for both the FAS and PP populations. Endpoints include:

- Change from baseline to end of Period 2 in body weight (kg), and
- Percent change/change from baseline in PWS Hyperphagia questionnaire for each of Overall Score (change from baseline only), 3 domains and individual scores (Period 2).
- Percent change/change from baseline in DEXA (Body Fat) and (Body Mass) for Period 2

Change from baseline in body weight over the 4-week double-blind dosing period will be assessed as a key secondary efficacy endpoint. Change in body weight during Period 2 will be tabulated by dose group.

Percent Change/Change from baseline in PWS Hyperphagia Questionnaire for each of Overall score (Change from baseline only), 3 domains and individual scores will be assessed as key secondary efficacy endpoints. Change and percent change in PWS during Period 2 will be tabulated by dose group.

Analyses for the key secondary endpoints will employ the similar methods used for the primary analyses (see Section 4.5.1.1).

4.5.2.2 Secondary endpoints

Additional secondary efficacy endpoints will be analysed for the FAS population only. Endpoints include:

- Body weight (kg): Percent Change/Change from baseline (Period 3) (Period 4)
- Body weight (kg): Percent Change/Change from baseline (Period 2/3) for continuous active and Placebo treatments
- PWS Hyperphagia Questionnaire: Percent Change/Change from baseline (Period 3) (Period 4)
- DEXA (body fat): Percent Change/Change from Baseline (Period 4)
- DEXA (body mass): Percent Change/Change from Baseline (Period 4)

The **Body weight (kg) percent change and change from baseline (Period 3) (Period 4)**, will be assessed for Period 3 and for Period 4.

The **Body weight (kg) percent change and change from baseline (Period 2/3)** for continuous active and Placebo treatments only (e.g. 4 treatment groups), will be assessed for Period 2 through Period 3.

[figure not shown]
The **PWS Hyperphagia Questionnaire percent change/change from baseline (Period 3) (Period 4)**, will be assessed for Period 3 and Period 4 with treatment groups corresponding to each period. Summaries will be generated for the Overall score, the 3 PWS domains, and individual questions.

The **DEXA (body fat) percent change/change from baseline (Period 4)**, will be assessed from end of Period 2 (Day 42) to end of Period 4 (Day 70), with treatment groups corresponding to these periods.

The **DEXA (body fat) percent change/change from baseline (Period 4)** will be assessed from end of Period 2 (Day 42) to end of Period 4 (Day 70), with treatment groups corresponding to these periods.

A similar model to that used for the primary endpoint analysis will be used for analysis of all secondary endpoints.

By-patient data listings will be provided.

[figure not shown]
The food related problem questionnaire Percent change/change from baseline (Period 2) (Period 3) (Period 4) will be assessed for each of these time periods between baseline and end of Periods 2, 3, and 4 for the respective treatment groups found in those time periods.

[figure not shown]
The Food-Related Problems Questionnaire is a tool specifically designed for patients with Prader-Willi Syndrome to rate preoccupation with food, impairment of satiety, difficulty with self-control and other food-related 'challenging' behavior. There are 16 questions on this 7-point Likert scale, with responses from 0 (never) to 6 (always), with a response of 7 (does not apply) included for 6 items on the scale. There are 3 open-ended questions. The maximum possible score is 96 for the total FRPQ, where a higher score indicates a 'worse' condition. See Appendix 3.

[figure not shown]
Along with the total item score, three (3) subscales will be presented for:

[figure not shown]
1. Preoccupation (items 1,5,15)
2. Impairment of satiety (items 8,9,13,14,16)
3. Composite negative behavior (2,4,8; 12,15; 3,7,14)

The individual item score and each subscale will be analyzed by each of the 3 periods, using descriptive statistics for visit and mean changes from baseline for each treatment group. If a single item in a factor is missing for a patient, that factor will be missing.

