5.3. Method of Assigning Patients to Treatment

Patients who qualify for the study will return to the site on Day -1 (e.g., randomization will formally take place at the end of the placebo-controlled run-in period, after compliance during the run-in period is assessed). Prior to randomization, the Investigator will ensure that the patient continues to meet inclusion and exclusion criteria, and perform all pre-dose procedures. Once a patient is determined to be eligible for randomization by the Investigator, the Investigator or the Investigator's research staff will randomize the patient according to a centralized randomization process.

Note all patients will be pre-randomized to their status/treatment group for the randomized withdrawal part of the protocol at the initial randomization.

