3.3.2 Secondary Efficacy Endpoints

[figure not shown]
3.3.2.1 Key secondary efficacy endpoint:

- Body weight (kg): Change from baseline (Period 2)
- PWS Hyperphagia Questionnaire: Percent Change/Change from baseline (Period 2)
 - Overall Score (Change from Baseline only – Period 2)
 - 3 domains
 - Hyperphagic Drive
 - Hyperphagic Behaviors
 - Hyperphagic Severity
 - Individual Questions
- DEXA (body fat): Percent Change/Change from Baseline (Period 2)
- DEXA (body mass): Percent Change/Change from Baseline (Period 2)

3.3.2.2 Additional Secondary endpoints are:

- Body weight (kg): Percent Change/Change from baseline (Period 3) (Period 4)

- Body weight (kg): Percent Change/Change from baseline (Period 2/3) for continuous active and continuous placebo treatments
- PWS Hyperphagia Questionnaire: Percent Change/Change from baseline (Period 3) (Period 4)
- DEXA (body fat): Percent Change/Change from Baseline (Period 4)
- DEXA (body mass): Percent Change/Change from Baseline (Period 4)

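### The Day 15 to Day 56 weight analysis uses only patients not switched at Day 42, which gives up some precision in one additional secondary endpoint

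*SAP*

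**What the plan says.** SAP 3.3.2 lists among the additional secondary endpoints "Body weight (kg): Percent Change/Change from baseline (Period 2/3) for continuous active and continuous placebo treatments". SAP 4.2.5 sets the interval: "Period 2/3: Day 15 through Day 56". SAP 4.5.2.2 restricts the analysis; the endpoint, "for continuous active and Placebo treatments only (e.g. 4 treatment groups), will be assessed for Period 2 through Period 3". The four groups are presumably continuous placebo and the three continuous doses.

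A model is planned as well as a table, because SAP 4.5.2.2 adds: "A similar model to that used for the primary endpoint analysis will be used for analysis of all secondary endpoints". The primary model is a mixed model for repeated measures (MMRM) with covariance statement "repeated visitnum / type=un subject=subjid". Each dose comparison "will be carried out via 1-sided statistical test at alpha=0.05, with no adjustment for multiplicity".

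Both documents split every Period 2 arm, placebo included, 1:1 at Day 42. On timing, Protocol 5.3 states that "all patients will be pre-randomized to their status/treatment group for the randomized withdrawal part of the protocol at the initial randomization". SAP 3.2 also fixes the assignment for Periods 1 to 3 at the initial randomisation.

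**The concern.** The patients left out took their randomised treatment throughout Period 2. They were weighed at Day 15 and Day 42, and at Day 28 if that visit was in clinic. Their switch was set before any Period 2 outcome existed and the treatment is blinded, so it cannot depend on how their weight changed. Their Day 56 weight on continued treatment is therefore missing completely at random, by design.

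An unstructured repeated-measures model can take such patients with the last visit missing. It uses their earlier weights through the within-patient correlation with Day 56. Dropping the patients forgoes that information.

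At stake is the precision of the only cumulative 6-week contrast with placebo, in a study that SAP section 1 says is meant to inform a Phase 3 design. For 2.5 mg that contrast rests on about 4 v 6 patients.

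**Working it through.** **Inputs.** SAP 4.1: "Assuming SD=1.1 for placebo and SD=2.3 for RM-493", effect 2.5 kg (also 2 kg), 12 v 12, one-sided alpha 0.05. SAP 3.1: about 20 then 16 patients, allocated 2:1:3. SAP 4.2: same doses pooled across halves, all placebo pooled. Assumed, because the documents give no values: the 4-week SDs and effect carry over to Day 56, and rho, the correlation between the Day 42 and Day 56 changes, lies between 0.3 and 0.9.

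**1. The plan's own figure.** Welch test: SE = sqrt(1.1²/12 + 2.3²/12) = 0.736 kg, df 15.8. Power is 94.5% at 2.5 kg and 83.0% at 2 kg, and the smallest significant difference is 1.29 kg. This matches the stated 94%, 83% and 1.3 kg, so Welch is used below.

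**2. Patients available.**

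| Arm | Randomised | Not switched |
|---|---|---|
| Placebo | 20×2/6 + 16×2/6 = 12 | 6 |
| 0.5 mg | 20×1/6 = 3.3 | 1.7 |
| 1.5 mg | 20×3/6 + 16×1/6 = 12.7 | 6.3 |
| 2.5 mg | 16×3/6 = 8 | 4 |
| Total | 36 | 18 |

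**3. Power at Day 56, continuous patients only.**
- 1.5 mg, 6 v 6: SE = sqrt(1.1²/6 + 2.3²/6) = 1.041, df 7.2. Power is 70% at 2.5 kg and 54% at 2 kg.
- 2.5 mg, 4 v 6: SE = sqrt(1.1²/6 + 2.3²/4) = 1.235, df 3.9. Power is 51% at 2.5 kg and 38% at 2 kg.

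**4. Adding the switched patients' Period 2 weights.** With a known regression slope of Day 56 on Day 42, the variance of an arm's Day 56 mean is sigma²[(1 − rho²)/n_cont + rho²/n_all]. With n_all = 2 n_cont this is sigma²/n_cont × (1 − rho²/2). In practice the slope is estimated from few patients, which costs some of the gain. Simulating Day 42 and Day 56 with half of Day 56 missing gives:

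| rho | 1 − rho²/2 | Simulated variance ratio | Change in variance |
|---|---|---|---|
| 0.3 | 0.955 | 1.03-1.07 | 3-7% loss |
| 0.5 | 0.875 | 0.93-0.96 | 4-7% gain |
| 0.7 | 0.755 | 0.80-0.81 | 19-20% gain |
| 0.8 | 0.68 | 0.71-0.72 | 28-29% gain |
| 0.9 | 0.595 | 0.61-0.62 | 38-39% gain |

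The ranges span the two dose comparisons and are approximate; a fresh simulation for this note agreed to within about one percentage point and showed no bias.

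**5. In power terms.** With tests calibrated to the same 5% one-sided error and a 2.5 kg effect, simulated power for 1.5 mg goes from about 70% to 76%, 85% and 90% at rho 0.5, 0.8 and 0.9. For 2.5 mg it goes from about 53% to 58%, 71% and 79%.

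**6. Where rho might lie.** Both changes share the Day 15 baseline and the first four of six weeks. Independent daily increments would give sqrt(27/41) = 0.81. This is an illustration, not a figure from the plan.

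**The case against.** The strongest reply is that little depends on this. The endpoint ranks below the primary and key secondary endpoints, in a pilot without multiplicity control whose conclusions are to be confirmed in Phase 3. SAP 4.2.5 says only that continuous-dosing data may be summarised. An observed-data comparison of patients who actually had six weeks of one treatment is unbiased and easy to read. That stands and limits the weight of the point. It does not remove it, since SAP 4.5.2.2 plans a model-based comparison and the same model can use more of the data.

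The gain also depends on an undocumented correlation and turns into a small loss if that is low. This stands too.

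The 2.5 mg starting power depends on the test. A pooled-variance t-test gives about 67%, but with 4 v 6 patients and unequal SDs its one-sided error is about 8%. The SAP's common unstructured covariance, fitted to continuing patients in all four arms, gives about 61%. The Welch figure of 51% is quoted because that test reproduces the plan's own power.

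Three stronger readings are tempting, and the documents do not support them:
- A reader might infer that the trial throws away valid Period 2 weights. They are omitted from this analysis only; SAP 4.5.1.1 and 4.5.2.1 use them.
- A reader might infer that the stated 94% and 83% are at risk. Those figures concern the 4-week comparison, and no power is claimed for Day 15 to Day 56.
- A reader might infer that this is the only randomised evidence after week 4. The Period 3 change (Day 42 to Day 56) is also analysed and compares randomised treatments in weeks 5 and 6.

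**Conclusion.** The point holds as a loss of efficiency in one additional secondary endpoint. About half of each arm is excluded from the cumulative 6-week weight comparison although those patients' earlier weights are informative about it. There is no bias, because the continuing patients are themselves a randomised subset.

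The saving in variance is modest at a correlation of 0.5 and worthwhile from about 0.7. It is never a full recovery: only at a correlation of 1 would the comparison be as precise as with Day 56 values from whole arms. These sizes rest on carrying the 4-week SDs and the 2.5 kg effect to Day 56, and on the assumed range of correlation.

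**What to change.** In SAP 4.5.2.2, fit the Period 2/3 weight MMRM to all FAS patients by Period 2 arm, with visits at Day 28 (where weighed in clinic), Day 42 and Day 56. Set Day 56 to missing for every patient switched at Day 42, so that no post-switch weight enters the contrast. Report the Day 56 LS mean difference of each dose against placebo, and keep the continuous-only results as a descriptive table.

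The cost is a SAP wording change and one altered data-selection step, with no new data, visits or patients. The statistical downside is a slight loss of precision if the Day 42/Day 56 correlation proves low.
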